1.7 Adverse Events

1.7.1 Common adverse events (AEs; greater than or equal to 10%)

Table 1-15 to Table 1-17 summarize the most commonly reported adverse events (AEs) regardless of relationship to TKI258 treatment, which are defined as events that occurred in $\geq 10\%$ of the patients who received TKI258 based on AE data in the clinical database as of the 10 September 2010 cutoff date.

The five most commonly reported non-laboratory AEs were nausea, fatigue/asthenia, diarrhea, vomiting and anorexia/decreased appetite for all 3 data groups (continuous daily dosing, global 5 days on/2 days off, and Japanese 5 days on/2 days off (study 1101)). Commonly reported AEs were reversible and manageable; most were mild or moderate in severity (CTCAE grade 1 or 2).

Preferred Term	<400mg (N=77) n (%)	400mg (N=51) n (%)	500-600mg (N=27) n (%)	All (N=155) n.(%)
Nausea	50(64.9)	40(78.4)	22(81.5)	112(72.3)
Fatigue	45(58.4)	37(72.5)	20(74.1)	102(65.8)
Diarrhoea	40(51.9)	37(72.5)	20(74.1)	97(62.6)
Vomiting	33(42.9)	28(54.9)	17(63.0)	78(50.3)
Anorexia	26(33.8)	14(27.5)	7(25.9)	47(30.3)
Headache	28(36.4)	7(13.7)	8(29.6)	43(27.7)
Constipation	19(24.7)	12(23.5)	9(33.3)	40(25.8)
Dyspnoea	21(27.3)	11(21.6)	8(29.6)	40(25.8)
Pyrexia	20(26.0)	10(19.6)	4(14.8)	34(21.9)
Dysgeusia	19(24.7)	13(25.5)	1(3.7)	33(21.3)
Rash	12(15.6)	15(29.4)	3(11.1)	30(19.4)
Weight decreased	10(13.0)	14(27.5)	5(18.5)	29(18.7)
Abdominal pain	15(19.5)	7(13.7)	5(18.5)	27(17.4)
Dizziness	9(11.7)	10(19.6)	8(29.6)	27(17.4)
Back pain	12(15.6)	8(15.7)	5(18.5)	25(16.1)
Anaemia	18(23.4)	3(5.9)	3(11.1)	24(15.5)
Dry mouth	12(15.6)	8(15.7)	3(11.1)	23(14.8)
Cough	11(14.3)	8(15.7)	3(11.1)	22(14.2)
Dehydration	6(7.8)	8(15.7)	8(29.6)	22(14.2)
Oedema peripheral	8(10.4)	6(11.8)	8(29.6)	22(14.2)
Pain in extremity	12(15.6)	4(7.8)	6(22.2)	22(14.2)
Urinary tract infection	9(11.7)	8(15.7)	5(18.5)	22(14.2)
Abdominal pain upper	7(9.1)	11(21.6)	3(11.1)	21(13.5)
Dyspepsia	9(11.7)	7(13.7)	3(11.1)	19(12.3)
Thrombocytopenia	11(14.3)	3(5.9)	5(18.5)	19(12.3)

Table 1-15 Commonly reported adverse events (occurring in greater than or equal to 10% patients) regardless of study drug relationship, by preferred term and treatment group (continuous daily dosing: studies 2101, 2102, 2103, 2104, 2105 and 2106)

	500mg (N=200)	600mg (N=5)	AII (N=205)	
Preferred Term	n (%)	n (%)	n (%)	
Diarrhoea	130(65.0)	3(60.0)	133(64.9)	
Nausea	121(60.5)	5(100)	126(61.5)	
Vomiting	111(55.5)	4(80.0)	115(56.1)	
Asthenia	89(44.5)	4(80.0)	93(45.4)	
Decreased appetite	76(38.0)	2(40.0)	78(38.0)	
Headache	47(23.5)	3(60.0)	50(24.4)	
Fatigue	48(24.0)	0(0.0)	48(23.4)	
Dyspnoea	43(21.5)	1(20.0)	44(21.5)	
Constipation	40(20.0)	0(0.0)	40(19.5)	
Dysgeusia	36(18.0)	1(20.0)	37(18.0)	
Abdominal pain	34(17.0)	1(20.0)	35(17.1)	
Rash	31(15.5)	2(40.0)	33(16.1)	
Hypertension	30(15.0)	1(20.0)	31(15.1)	
Weight decreased	29(14.5)	1(20.0)	30(14.6)	
Abdominal pain upper	29(14.5)	0(0.0)	29(14.1)	
Cough	26(13.0)	3(60.0)	29(14.1)	
Anaemia	26(13.0)	0(0.0)	26(12.7)	
Dry skin	25(12.5)	1(20.0)	26(12.7)	
Oedema peripheral	26(13.0)	0(0.0)	26(12.7)	
Dizziness	23(11.5)	0(0.0)	23(11.2)	
Dry mouth	23(11.5)	0(0.0)	23(11.2)	
Pyrexia	19(9.5)	3(60.0)	22(10.7)	
Stomatitis	22(11.0)	0(0.0)	22(10.7)	
Myalgia	20(10.0)	1(20.0)	21(10.2)	
*CTCAE version 4.0 was used in these studies				

Table 1-16 Commonly reported adverse events (occurring in greater than or equal to 10% patients) regardless of study drug relationship, by preferred term and treatment group (5 days on/2 days off dosing: study 2107, 2112*, 2201*, 2202, 2204*)

• /	<300mg (N=6)	300mg (N=7)	400mg (N=9)	All (N=22)
Preferred Term	n (%)	n (%)	n (%)	n (%)
Diarrhoea	5(83.3)	5(71.4)	9(100)	19(86.4)
Nausea	3(50.0)	6(85.7)	8(88.9)	17(77.3)
Decreased appetite	2(33.3)	5(71.4)	7(77.8)	14(63.6)
Fatigue	4(66.7)	4(57.1)	5(55.6)	13(59.1)
Vomiting	1(16.7)	5(71.4)	7(77.8)	13(59.1)
Blood alkaline phosphatase increased	2(33.3)	5(71.4)	5(55.6)	12(54.5)
Hypertension	1(16.7)	4(57.1)	4(44.4)	9(40.9)
Lymphopenia	2(33.3)	5(71.4)	2(22.2)	9(40.9)
Weight decreased	0(0.0)	3(42.9)	5(55.6)	8(36.4)
Headache	1(16.7)	0(0.0)	5(55.6)	6(27.3)
Hepatic function abnormal	2(33.3)	1(14.3)	3(33.3)	6(27.3)
Hypertriglyceridaemia	0(0.0)	2(28.6)	4(44.4)	6(27.3)
Hypoalbuminaemia	0(0.0)	3(42.9)	3(33.3)	6(27.3)
Rash	1(16.7)	3(42.9)	2(22.2)	6(27.3)
Blood triglycerides increased	2(33.3)	1(14.3)	2(22.2)	5(22.7)
Cancer pain	2(33.3)	2(28.6)	1(11.1)	5(22.7)
Dysgeusia	1(16.7)	2(28.6)	2(22.2)	5(22.7)
Leukopenia	1(16.7)	2(28.6)	2(22.2)	5(22.7)
Pyrexia	1(16.7)	2(28.6)	2(22.2)	5(22.7)
Stomatitis	0(0.0)	0(0.0)	5(55.6)	5(22.7)
White blood cell count decreased	0(0.0)	2(28.6)	3(33.3)	5(22.7)
Alanine aminotransferase increased	1(16.7)	0(0.0)	3(33.3)	4(18.2)
Constipation	2(33.3)	2(28.6)	0(0.0)	4(18.2)
Neutrophil count decreased	0(0.0)	2(28.6)	2(22.2)	4(18.2)
Palmar-plantar erythrodysaesthesia syndrome	0(0.0)	2(28.6)	2(22.2)	4(18.2)
Anaemia	0(0.0)	2(28.6)	1(11.1)	3(13.6)
Aspartate aminotransferase increased	1(16.7)	0(0.0)	2(22.2)	3(13.6)
Blood albumin decreased	1(16.7)	1(14.3)	1(11.1)	3(13.6)
Blood fibrinogen increased	1(16.7)	1(14.3)	1(11.1)	3(13.6)
C-reactive protein increased	0(0.0)	1(14.3)	2(22.2)	3(13.6)
Dizziness	0(0.0)	2(28.6)	1(11.1)	3(13.6)
Dry mouth	1(16.7)	0(0.0)	2(22.2)	3(13.6)
Haemoglobin decreased	0(0.0)	1(14.3)	2(22.2)	3(13.6)
Myalgia	0(0.0)	0(0.0)	3(33.3)	3(13.6)
Neutropenia	0(0.0)	1(14.3)	2(22.2)	3(13.6)
Pharyngitis	0(0.0)	1(14.3)	2(22.2)	3(13.6)
Platelet count decreased	0(0.0)	1(14.3)	2(22.2)	3(13.6)
Thrombocytopenia	0(0.0)	1(14.3)	2(22.2)	3(13.6)

Table 1-17 Commonly reported adverse events (occurring in greater than or equal to 10% patients) regardless of study drug relationship, by preferred term and treatment group (5 days on/2 days off dosing: study 1101)

1.7.2 CTCAE grade 3 and grade 4 adverse events regardless of study drug relationship (greater than or equal to 2%)

The majority of these events were grade 3 across all dosing regimens. In the continuous dosing regimen studies, grade 4 events included 5 cases of fatigue, 2 cases of pyrexia, 1 case of deep vein thrombosis, 5 cases of pulmonary embolism, 2 cases of neutropenic sepsis, and 1 case of pain in extremity. In the global 5 days on/2 days off dosing regimen studies, grade 4 events included 3 cases of pumonary embolism and 1 case of stomatitis. In the Japanese 5 days on/2 days off dosing regimen study (1101), there were no grade 4 events for these AEs.

1.7.3 Laboratory Data

The majority of the hematology laboratory abnormalities were grade 1 or 2 events across all dosing regimens. In continuous dosing regimen studies, five patients (3.5%) had grade 4 hemoglobin values, 7 patients (7.4%) had grade 4 ANC values, 19 patients (14.6%) had grade 4 platelet counts, and 9 patients (6.9%) had grade 4 WBC values during study participation.

The relatively higher incidence rate of grade 3/4 hematology abnormalities in the continuous daily dosing regimen was mainly due to acute myeloid leukemia (study 2102) and multiple myeloma (studies 2103 and 2104) patients. In global 5 days on/2 days off dosing regimen studies, 2 patients (1.3%) had grade 4 ANC values, 1 patient (0.5%) had grade 4 platelet counts, and no patients had grade 4 hemoglobin or white blood counts during study participation. Also, one patient (4.5%) had grade 4 hemoglobin in the Japanese 5 days on/2 days off dosing regimen study and no patients had grade 4 ANC, platelet or white blood cell counts during study participation.

The majority of the chemistry laboratory abnormalities were also grade 1 or 2 events across all dosing regimens. In continuous dosing regimen studies, only 1 patient (0.7%) had grade 4 creatinine value and 2 patients (1.6%) had grade 4 triglyceride values. There were no grade 4 abnormalites observed in cholesterol or amylase laboratory values in the continuous dosing regimen. In global 5 days on/2 days off dosing regimen studies, 2 patients (1.2%) had grade 4 triglycerides and 2 patients (1.1%) had grade 4 cholesterol values. There were no grade 4 abnormalites observed in amylase or creatinine laboratory values in this dosing regimen. Also, there were no grade 4 chemistry laboratory abnormalities observed in Japanese patients. The majority of the liver function test laboratory abnormalities were also grade 1 or 2 events across all dosing regimens. In the continuous dosing regimen studies, there were no grade 4 laboratory values observed in AST, ALT, total bilirubin or alkaline phosphatase. In global 5 days on/2 days off dosing regimen studies, there were no grade 4 AST laboratory values;

however, 1 patient (0.5%) had a grade 4 ALT value, 1 patient (1.1%) had a grade 4 total bilirubin value, and 3 patients (1.6%) had a grade 4 alkaline phosphatase values. In the Japanese 5 days on/2 days off dosing regimen study, only 1 patient (4.5%) had grade 4 total bilirubin values and no grade 4 values were observed in the AST, ALT or alkaline phosphatase values during study participation.

1.7.4 Hepatic dysfunction as defined by laboratory criteria As of the 10 September 2010 data cut-off, there were 12 cases with hepatic dysfunction, defined as total bilirubin >2X ULN and AST or ALT > 3X ULN. From the Novartis perspective, in 6 of these cases, data available do not provide any evidence supporting a causal relationship of hepatic dysfunction and dovitinib treatment. The cause of liver injury in these patients was progression of underlying metastatic liver disease, with signs suggestive of pre-existing cholestatic liver injury in 5 out of 6 patients.

For 6 out of 12 patients, a contribution of dovitinib treatment to liver injury cannot be excluded, based on time relationship of onset or worsening of elevated enzyme activities to study treatment and improvement of enzyme activities after stop/interruption of treatment.

None of the above cases qualifies as a "Hy's law" case (Rueben 2004). All of the cases demonstrate a clear cholestatic component, only 2 of 12 cases would qualify as mixed type cholestatic/hepatocellular injury, the remaining 10 cases are of cholestatic injury type. Moreover, factors confounding any qualification as "Hy's law" were present in all 12 patients in terms of underlying disease (malignancy, 10 of 11 solid tumor cases with liver metastases at baseline), and in 10 of 12 patients in terms of concomitant medication. One heavily pre-treated, advanced breast cancer patient with liver, bone and lymph nodes metastases was assessed by the investigator as having drug-related cholestatic hepatic injury leading to death. Confounding factors were present in this fatal case including liver metastases and concomitant medications. Of the remaining 11 patients: 1 patient remains on study, for 1 patient there is no available survival data, and in 9 patients, the deaths were due to disease progression.

2.0 STUDY OBJECTIVES

2.1 Primary Objective

The primary objective of this study is:

- To estimate overall survival and early response as characterized by a drop in PSA
- To identify the PSA modulation in 40 selected patients with advanced prostate cancer, and to correlate PSA Modulation with changes in bone remodeling markers.

Secondary Objectives

The secondary objectives of this study are:

- To estimate the objective tumor response rate for subjects with measurable disease at baseline.
- To explore the potential association between serum PSA and bone turnover markers with bone marrow FGF R 1 and FGF9 while on TKI 258
- To explore the predictive values of baseline FGF R 1, FGF9, and FGF signaling in serum and those in the bone marrow before and during treatment with TKI258
- To identify candidate mRNA gene expression changes in bone marrow biopsy aspirate following treatment with TKI258
- To collect and archive bone marrow biopsies and aspirates, serum and plasma in study patients for later hypothesis generating associations
- To explore FGF R expression following eight weeks of TKI 258.

3.0 INVESTIGATIONAL PLAN

3.1 Overall Study Design and Plan

This is an observational study to explore the effect of TKI258 therapy on bone turnover markers (serum bone specific alkaline phosphatase and urinary N-telopeptides), and expression of FGF R 1, on both tumor and host cell compartments in bone marrow.

3.2 Study Duration and Dates

In this oncology study, patients will receive study treatment until clinical disease progression.

4.0 STUDY POPULATION SELECTION

Approximately 40 medically or surgically castrated male patients with metastatic castrationresistant prostate cancer (CRPC) will be enrolled from one study site.

4.1 Inclusion Criteria

Each patient must meet the following criteria to be enrolled in this study.

- 1) Histologically proven adenocarcinoma of the prostate with evidence for skeletal metastases on bone scan and/or CT scan.
- 2) Eastern Cooperative Oncology Group (ECOG) performance status ≤ 2 . (Karnofsky Performance Status $\geq 50\%$) (Appendix F)
- 3) Serum testosterone levels \leq 50ng/ml

- 4) Ongoing gonadal androgen deprivation therapy with LHRH analogues or orchiectomy. Patients, who have not had an orchiectomy, must be maintained on standard dosing of LHRH analogue therapy at appropriate frequency for the duration of the study
- 5) Progression of disease despite androgen ablation (either documented osseous or soft tissue metastatic disease progression or by PSA criteria progression).
 - a) Definition of Progressive disease by PSA evidence: a PSA level of at least 5 ng/ml which has risen on at least 2 successive occasions, at least 2 weeks apart. The participant will need a baseline test and a test to show that the PSA has increased.
- 6) Discontinue diethylstilbestrol (DES) for ≥ 4 weeks and antiandrogens ≥ 6 weeks prior to study drug.
- 7) Discontinue any steroids prescribed to specifically treat prostate cancer (for e.g as a secondary hormonal manipulation or for cord compression) ≥ 4 weeks prior to study drug. Steroids chronically prescribed for a non-cancer-related illness (e.g. asthma or COPD) that is well controlled with medical management are permissible to an equivalent of ≤10 mg Prednisone daily.
- 8) Antiandrogen Withdrawal: Patients who are receiving an antiandrogen as part of primary androgen ablation must demonstrate disease progression following discontinuation of antiandrogen. Disease progression after antiandrogen withdrawal is defined as 2 consecutive rising PSA values, obtained at least 2 weeks apart, or documented osseous or soft tissue progression.
- 9) For patients receiving flutamide, at least one of the PSA values must be obtained 4 weeks or more after flutamide discontinuation.
- 10) For patients receiving bicalutamide or nilutamide, at least one of the PSA values must be obtained 6 weeks or more after antiandrogen discontinuation
- 11) Laboratory Requirements:
 - Adequate adrenal function (absence of symptoms or electrolyte imbalances that indicate adrenal insufficiency).
 - WBC count \geq 3,000/µl
 - Absolute Neutrophil Count (ANC) \geq 1,500/µl
 - Hemoglobin ≥ 8.0 g/dL independent of transfusion
 - Platelet count \geq 75,000/µL
 - Serum albumin $\geq 3.0 \text{ g/dL}$
 - Serum creatinine < 1.5 x ULN or a calculated creatinine clearance > 60 mL/min
 - Serum potassium \geq 3.5 mmol/L
- 12) No evidence of chronic or acute DIC (Disseminated Intravascular Coagulation) or bleeding tendency and no angina at rest.
- 13) Patient must be willing and able to comply with protocol requirements. All patients must sign an informed consent indicating that they are aware of the investigational nature of this study. Patients must also have signed an authorization for the release of their protected health information.

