1.2 Background /Rationale

Androgen deprivation (AD) therapy induces a remission in 80% to 90% of patients with advanced prostate cancer and results in a median progression-free survival of 12 to 33 months, at which time; an androgen-independent phenotype usually emerges.

Androgen deprivation can be achieved surgically with orchiectomy, or medically using some form of drug treatment that lowers serum testosterone. Medical castration is commonly achieved with luteinizing hormone - releasing hormone (LHRH) agonists (for example, Lupron). The conventionally accepted definition of castration is a serum concentration of testosterone to less then 50 ng/dl. Additional antiandrogen therapies include classes of agents that: (1) block testosterone activity (for example, bicalutimide), (2) block adrenal synthesis of testosterone (for example, ketoconazole); or (3) synthetic estrogens (for example, DES). These agents are generally used to treat patients who demonstrate PSA and/or clinical progression while on Lupron monotherapy. Because many cancers continue to respond to these "second-line" hormonal strategies (given either singly or in combination) despite castrate levels of testosterone, this clinical state is referred to "castrate-resistant" disease (as opposed to "hormone-refractory" disease).

After failure of anti-androgen therapy, patients with castrate-resistant prostate cancer are routinely treated with cytotoxic chemotherapies. Two randomized trials testing docetaxel based regimens demonstrated PSA responses ranging from 40 to 50% but only a modest survival benefit of ~ 2 to 3 months. Chemotherapy was also associated with significant toxicities, including grade 3/4 neutropenia (~30%), infections (~6%), anemia (~5%), fatigue (~5%), dyspnea (~3%), nausea (~3%), diarrhea (~2%) and neuropathy (~1.5%). Based on these data, docetaxel-based chemotherapy is an option for patients with castrate-resistant disease but is not considered "standard of care". Current research efforts are now focused on identifying novel molecularly targeted therapies that will reduce morbidity and mortality from castrate-resistant disease and obviate (or at least delay) the use of cytotoxic chemotherapy.

The propensity for prostate cancer to metastasize to the skeleton has led investigates to speculate that the tumor microenvironment and the stromal-epithelial interactions within bone are critical for prostate cancer progression. Furthermore, the development

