6.10 Other Study Procedures

Supportive care medications are permitted with their use following institutional guidelines. As mentioned in the eligibility criteria, patients must have ongoing gonadal androgen deprivation therapy with LHRH analogues or orchiectomy. Patients, who have not had an orchiectomy, must be maintained on effective LHRH analogue therapy for the duration of the trial.

The concurrent administration of other anticancer therapy, including cytotoxic, hormonal (except LHRH agonists), or immunotherapy is prohibited during study treatment phase. Use of other investigational drug therapy for any reason is prohibited.

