7.1 Screening Period (Days –30 to Day 1)

The following activities/procedures will be conducted during the screening period which may occur within 30 days prior to registration the following baseline evaluations shall be performed:

- Complete medical history must be available in the patient's medical record
- Chest X-ray
- CT or MRI scans of the pelvis and abdomen.
- Bone Scan
- Baseline (pre-treatment) bone marrow biopsy and aspiration within 30 days prior to registration. The specimens will be evaluated by pathology. A portion of bone marrow will be banked for bone marker testing. Patients who have undergone a bone marrow aspirate and biopsy outside the context of this clinical trial are eligible for the trial and may elect not to repeat these baseline studies if the samples were collected within 12 weeks prior to initiation of TKI258 therapy. If a portion of the tissue collected from a previous bone marrow aspirate and biopsy was banked for future use under Lab02-152, Lab03-0320, or another GU clinical trial, the tissue will be requested for this timepoint.
- Electrocardiogram (ECG)
- Echocardiogram or MUGA scan
- 7.2 Screening Period (Days –14 to Day 1)

The following activities/procedures will be conducted during the screening period which may occur within 14 days prior to registration the following baseline evaluations shall be performed:

- Interim medical history including demographics
- Oncology history
- Physical examination
- Vital signs including blood pressure, heart rate, respiratory rate, oral body temperature, weight and height.
- List of concurrent medications and baseline adverse events
- Assessment of ECOG Performance Status
- Laboratory testing:
 - CBC with differential/platelets
 - Serum chemistry must include: BUN, creatinine, total bilirubin, albumin, SGOT [AST], SGPT [ALT], GGT, LDH, amylase, lipase, alkaline phosphatase, fasting glucose, calcium, sodium, magnesium, phosphorus, and potassium
 - PSA assessment.
 - Serum testosterone and DHT levels.
 - Bone Specific Alkaline Phosphatase
 - Blood for Biomarker Studies
 - N-telopeptides in urine

Correlative Studies: Assessment of serum and bone marrow aspirate androgen levels, plus additional serum/plasma banking.

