Historical Experience and Goals: Based on the historical experience in which the mean survival time was 8 months, under a Bayesian model we assume that the unadjusted mean survival time with TKI258 follows an uninformative inverse gamma with mean 8 and variance 1000, equivalently with scale parameter 2.064 and shape parameter 8.512, denoted mE ~ IG(2.064, 8.512). A mean survival time on average > 10 months would be considered promising evidence of anti-disease activity. Formally, assuming that the historical mean survival mH ~ IG(52, 400), TKI258 will be considered promising if, based on the data from the trial, Pr(mE > mH | data) > .95. The planned sample size is 40 patients, with an anticipated accrual rate of 3 patients per month. In addition, the relationships between several potential prognostic covariates and the above clinical outcomes will be explored, as described below.

Monitoring Rules: No early stopping rule in terms of the probability of PSA response will be employed because it is not known whether blocking the stromal-epithelial interactive pathway (SE-pathway) will be related to clinical benefit. Consequently, it may be the case that PSA does not drop but survival time is prolonged due to inhibition of disease progression by TKI258. Given the short survival time of these patients and anticipated accrual rate of 3 patients per month, it will not be feasible to implement an early stopping rule in terms of observed survival times. However, based on an historical rate of 20% grade 3 or 4 toxicity with standard therapies, it will be assumed that p = Prob(grade 3 or 4 with TKI258) follows a beta prior with parameters (.20, .80). Using the method of Thall and Suung (26), based on the observed toxicity data, accrual to the trial will be stopped early if Pr(p > .20 | data) > .95, with this rule applied after successive cohorts f size 5. This rule says to stop the trial if [# patients with a grade 3 or 4 toxicity]/[# patients evaluated] is greater than or equal to 3/5, 5/10, 7/15, 8/20, 9/25, 11/30, 12/35. The operating characteristics of this rule are summarized in the following table.

True Prob(toxicity)	Prob(Stop Early)	Achieved Sample Size
		$25^{\text{th}}, 50^{\text{th}}, 75^{\text{th}}$ percentiles

.10	.01	40 40 40
.20	.11	40 40 40
.30	.47	20 40 40
.40	.86	5 15 25

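### Inclusion criterion 3 sets the testosterone limit in ng/ml, 100 times the protocol's own castration definition in ng/dl, so as written it does not screen for castrate status

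*Combined protocol and SAP*

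**What the plan says.** Section 1.2 (Background/Rationale) states: "The conventionally accepted definition of castration is a serum concentration of testosterone to less then 50 ng/dl". Section 4.0 describes the intended sample as "medically or surgically castrated male patients" with metastatic castration-resistant disease, about 40 of them from one site.

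Section 4.1, criterion 3, then sets the only numeric testosterone limit among the eligibility criteria: "Serum testosterone levels \leq 50ng/ml".

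Other text bears on castrate status without giving a level:

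- Criterion 4 requires ongoing LHRH analogue therapy or orchiectomy.
- Criterion 5 requires "Progression of disease despite androgen ablation".
- Criteria 8 to 10 deal with progression after antiandrogen withdrawal.
- Section 6.10 says that men without orchiectomy "must be maintained on effective LHRH analogue therapy for the duration of the trial".
- The screening laboratory list in section 7.2 includes "Serum testosterone and DHT levels", with no threshold or unit.

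On the analysis side, section 10.0 names survival and PSA response as the two primary outcomes. It derives its survival benchmark as follows: "Based on the historical experience in which the mean survival time was 8 months".

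**The concern.** The eligibility limit and the definition it should enforce carry the same number in different units. Read literally, criterion 3 passes every value from 50 to 5,000 ng/dl, all of which fail the definition in section 1.2. The one numeric check on castrate status therefore does not do its job. It is also the limit against which eligibility is formally checked, since section 4.1 makes every listed criterion mandatory.

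The trial is a single arm of 40, so what the sample represents rests on the entry criteria. A man whose testosterone is not suppressed by his LHRH therapy could show a PSA change that reflects a change in suppression on study, not drug activity. His survival might also differ from that of the patients behind the 8-month historical mean. That second point is an inference, because section 10.0 does not describe the historical group.

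**Working it through.** **Unit comparison**

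| Source | As written | In ng/dl | In ng/ml |
|---|---|---|---|
| Section 1.2, castration definition | < 50 ng/dl | < 50 | < 0.5 |
| Section 4.1, criterion 3 | ≤ 50 ng/ml | ≤ 5,000 | ≤ 50 |

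Conversion: 50 ng/ml × 100 ml/dl = 5,000 ng/dl. Ratio: 5,000 / 50 = 100. In a common unit the two limits would agree except at exactly 50, where one inequality is strict and the other is not.

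**Does anything else supply the limit?** Criterion 4 specifies a treatment, not demonstrated suppression. Criteria 5 and 8 to 10 specify progression, which can also occur in a man whose testosterone is not suppressed. Section 4.0 describes the population without a level. Section 6.10 asks for effective LHRH therapy, but section 7.4 lists no serum testosterone test during treatment that would give the word a measured meaning. The schedule in Appendix J is not in the supplied text. Androgen testing does appear in section 7.2 (serum and marrow, correlative), section 7.4.5 (marrow, around week 8) and section 7.5 (serum and marrow, final visit), but none of it carries a cut-off.

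**Scale on PSA response.** One patient in 40 is 1/40 = 2.5 percentage points, in either direction. The plan sets no decision threshold for this outcome.

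**Scale on survival, for orientation only.** The plan has no figure of its own that depends on the testosterone limit, so there is nothing to reproduce. The survival rule in section 10.0 shows how far one patient could count.

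- Inputs from section 10.0: prior mE ~ IG(2.064, 8.512), historical mH ~ IG(52, 400), 40 patients, TKI258 promising if Pr(mE > mH | data) > .95.
- With all 40 deaths observed and total follow-up of T months, the posterior is mE ~ IG(42.064, 8.512 + T).
- Pr(mE > mH | data) is then the F distribution function with 2 × 42.064 = 84.128 and 2 × 52 = 104 degrees of freedom, evaluated at [(8.512 + T)/400] × [52/42.064].
- At T = 400 (sample mean 10 months) this gives .871.
- It reaches .95 at T = 445.75, a sample mean of 445.75/40 = 11.14 months.
- If one such man's survival differs by d months, the sample mean moves by d/40. For assumed d of 6, 12 and 24 months the shifts are 0.15, 0.30 and 0.60 months, up or down.

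The values of d are assumptions. Neither they nor the number of such men is in the documents.

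**The case against.** The best reply is that this is a plain unit slip which site staff would read as intended, and that castrate status is covered elsewhere. Section 1.2 links castrate-resistant disease to castrate levels of testosterone, and section 4.0 limits the population to castrated men with that disease. A wrongly admitted man would have to be on standard LHRH dosing, be progressing, and still be unsuppressed; men with orchiectomy are largely outside the concern. No design calculation uses the figure. The per-patient shifts in PSA rate and mean survival would apply to any one patient who deviates for any reason, so they are not evidence of harm from this slip.

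Much of this stands. The exposed group is narrow and of unknown size, the effect figures give scale only, and comparability with the historical group cannot be tested from the documents. A unit slip is the probable cause, though nothing in the text confirms it.

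The objection does not remove the contradiction. Section 4.0 describes a population and is not a numbered criterion. If the treatment requirement were sufficient, criterion 3 would have no purpose. A man at 200 ng/dl meets criterion 3 and fails section 1.2, so two careful readers could reach opposite eligibility decisions.

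**Conclusion.** The concern holds. Criterion 3 contradicts the protocol's own definition of castration by a factor of 100, and no other section supplied gives a level that would repair it. It is a unit error in a binding entry criterion, not a failed design calculation: no sample-size or operating-characteristic figure changes.

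The practical effect is probably confined to men on LHRH therapy with unsuppressed testosterone. How many there are, and the size and direction of any bias, cannot be determined from the documents. The contradiction should be fixed because the criterion defines who is in a 40-patient single-arm trial.

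**What to change.** 1. Reconcile section 1.2 and criterion 3 of section 4.1 so that the castration definition and the eligibility limit use the same unit and the same inequality. The choice of limit is for the sponsor and investigators.
2. For patients already enrolled, compare the screening testosterone collected under section 7.2 with the reconciled definition, and report how many fall outside it.
3. If any do, report PSA response and survival with and without them. If none do, say so; that documents that the population was the intended one on this point.

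The cost is a short eligibility amendment, a review of laboratory values already held and, only if needed, one sensitivity analysis. No new data collection is required.
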